#### **Inclusion Criteria for UC Cohort 5 (Progression while on Anti-PD-1/PD-L1 Therapy):**

- Patients in UC Cohort 5 must meet the following criteria for study entry:
- Histologically or cytologically documented locally advanced (T4b, any N; or any T, N2–N3) or metastatic (M1, Stage IV) urothelial bladder cancer (also termed transitional cell carcinoma, urothelial carcinoma, or carcinoma of the urinary tract; including renal pelvis, ureters, urinary bladder, and urethra)

Patients with mixed histologies are required to have a dominant transitional cell pattern.

- Locally advanced bladder cancer must be inoperable on the basis of involvement of pelvic sidewall or adjacent viscera (clinical stage T4b) or bulky nodal metastasis (N2–N3)

Transurethral resection for bladder tumor (TURBT) specimens must contain a muscle-invasive component (i.e., T2 or greater) or the bladder tumor as verified by local pathology review. If the TURBT specimens do not contain a muscle-invasive component, then specimens obtained at the time of cystectomy, nephroureterectomy, or metastatic spread (i.e., a sample from a metastatic lesion) will be required prior to enrollment.

- Disease progression during or following treatment with at least one platinum-containing regimen for inoperable, locally advanced or metastatic urothelial bladder cancer or disease recurrence
  - Patients who received prior adjuvant/neoadjuvant chemotherapy and progressed within 12 months of treatment with a platinum-containing adjuvant or neoadjuvant regimen are eligible.
  - Patients who have received one cycle of a platinum-containing regimen but discontinued because intolerable toxicity may also be eligible.
  - Patients with disease progression following chemoradiotherapy must demonstrate progression outside the prior radiotherapy port.
- Progression while on a prior anti-PD-1/PD-L1 therapy in the recurrent or metastatic setting
  - Patients are also eligible if they had disease progression on or within 6 months of the last dose of anti-PD-1/PD-L1 therapy in the adjuvant setting
- Prior treatment with T-cell co-stimulating or immune checkpoint blockade therapies, and combinations including anti-CTLA-4, anti-PD-1/PD-L1 therapeutic antibodies are allowed
- Patients are eligible if they received no more than three lines of therapy in the advanced, metastatic setting

#### **4.1.3.3 RCC Cohorts**

##### **Inclusion Criteria for RCC Cohort 3 (Anti-PD-1/PD-L1 Treatment-Naive Patients):**

Patients in RCC Cohort 3 must meet the following criteria for study entry:

- Histological confirmation of advanced or metastatic RCC with a clear-cell component
- Prior cytokine therapy (e.g., IL-2, IFN- $\alpha$ ), vaccine therapy, or treatment with cytotoxic agents is allowed.
- Patients must have received at least one but no more than two total prior systemic treatment regimens in the advanced or metastatic setting.

##### **Inclusion Criteria for RCC Cohort 6 (Progression while on Anti-PD-1/PD-L1 Therapy):**

- Patients in RCC Cohort 6 must meet the following criteria for study entry:
- Histological confirmation of advanced or metastatic RCC with a clear-cell component
- Prior cytokine therapy (e.g., IL-2, IFN- $\alpha$ ), vaccine therapy, or treatment with cytotoxic agents is allowed.
- Progressed while on prior anti-PD-1/PD-L1 therapy in the recurrent or metastatic setting

Patients are also eligible if they had disease progression on or within 6 months of the last dose of anti-PD-1/PD-L1 therapy in the adjuvant setting.

- Prior treatment with T-cell co-stimulating or immune checkpoint blockade therapies, and combinations including anti-CTLA-4, anti-PD-1/PD-L1 therapeutic antibodies are allowed.
- Patients are eligible if they received no more than three lines of therapy in the advanced/metastatic setting.

#### **4.1.3.4 Biopsy Cohort 7**

- Patients must have histologically confirmed non-melanoma, non-hematologic solid tumor.
- Patients must have metastatic or locally advanced disease that is not amenable to local treatment with curative intent.
- Measurable disease according to RECIST v1.1
- Patients in this cohort must have received a minimum of two cycles of anti-PD-1 or anti-PD-L1 therapy.
- Patients in this cohort must have progressed during or after anti-PD-1 or anti-PD-L1 therapy within 12 weeks before study start.
- Patients in this cohort must meet criteria for primary or secondary resistance to an anti-PD-1 or anti-PD-L1 agent as outlined below:

Primary resistance is defined as progressive disease, according to RECIST v1.1, as best response

Secondary resistance is defined as progressive disease after initial confirmed response according to RECIST v1.1

- Patients in this cohort must have received anti-PD-1 or anti-PD-L1 therapy as the most recent treatment.
- Patients in this cohort must consent to undergo tumor biopsies of accessible lesions before and during treatment for biomarker analyses.
- Patients in this cohort must have at least two accessible lesions that are amenable to excisional or core-needle biopsy with acceptable risk of a major procedural complication. Exceptions may be made following discussion with Medical Monitor.

## **4.2 METHOD OF TREATMENT ASSIGNMENT AND BLINDING**

This is an open-label trial. After written informed consent has been obtained and eligibility has been established, each patient will be assigned an identification number and be enrolled to the appropriate cohort through use of an interactive voice or Web-based response system (IxRS).

## **4.3 STUDY TREATMENT**

The investigational medicinal products (IMPs) for this study are cobimetinib and atezolizumab.

### **4.3.1 Formulation, Packaging, and Handling**

#### **4.3.1.1 Cobimetinib**

Cobimetinib will be supplied as 20-mg, film-coated tablets packaged in blister packs (21 tablets per pack; 3 packs per box) for oral administration.

For information on the formulation and handling of cobimetinib, see the Cobimetinib Investigator's Brochure and pharmacy manual.

#### **4.3.1.2 Atezolizumab**

Atezolizumab will be supplied as sterile liquid in single-use, 20-mL glass vials. The vial is designed to deliver 20 mL (1200 mg) of atezolizumab solution, but it may contain more than the stated volume to enable delivery of the entire 20-mL volume. Administration of 14 mL of atezolizumab solution from a 1200-mg vial contains an 840-mg dose.

For information on the formulation and handling of atezolizumab, refer to the Atezolizumab Investigator's Brochure and pharmacy manual.

### **4.3.2 Dosage, Administration, and Compliance**

#### **4.3.2.1 Cobimetinib**

Patients will receive cobimetinib 60 mg (3 tablets of 20 mg each) orally QD on Days 1–21 of each 28-day cycle in all cohorts. This 4-week period is considered a treatment cycle.

Cobimetinib should be taken at the same time every day. It can be taken with or without food. If a dose of cobimetinib is missed or if vomiting occurs when the dose is taken, patients may resume dosing with the next scheduled dose.

Guidelines for dosage modification and treatment interruption or discontinuation of cobimetinib are provided in Section [5.1.3.1](#).

Any dose modification should be noted on the Study Drug Administration electronic Case Report Form (eCRF). Cases of overdose, medication error, drug abuse, or drug misuse, along with any associated adverse events, should be reported as described in Section [5.4.4](#).

#### **4.3.2.2 Atezolizumab**

Atezolizumab will be given at a fixed dose of 840 mg by IV infusion on Days 1 and 15 of each 28-day cycle. A 28-day period is considered a treatment cycle.

Patients in the biopsy cohort, Cohort 7, will receive the first dose of atezolizumab of 840 mg by IV infusions on Day 15 of Cycle 1. Thereafter, they will receive atezolizumab 840 mg IV infusion Q2W on Days 1 and 15 of Cycle 2 and all subsequent cycles.

Administration of atezolizumab will be performed in a monitored setting where there is immediate access to trained personnel and adequate equipment and medicine to

manage potentially serious reactions. For anaphylaxis precautions, see [Appendix 7](#). Atezolizumab infusions will be administered per the instructions outlined in [Table 3](#).

**Table 3 Administration of First and Subsequent Atezolizumab Infusions**

First Infusion	Subsequent Infusions
Premedication is not allowed.	If patient experienced IRR during any previous infusion, pre-medication with antihistamines, antipyretics, and/or analgesics may be administered for subsequent doses at the discretion of the treating physician.
Record vital signs (pulse rate, respiratory rate, blood pressure, and temperature) within 60 minutes before starting infusion.	Record patient's vital signs (pulse rate, respiratory rate, blood pressure, and temperature) within 60 minutes before starting infusion.
Infuse atezolizumab (one vial in 250 mL of NaCl) over 60 ( $\pm$ 15) minutes.	If the patient tolerated the first infusion well without infusion-associated adverse events, the second infusion may be delivered over 30 ( $\pm$ 10) minutes.
Record vital signs (pulse rate, respiratory rate, blood pressure, and temperature) during the infusion or after the infusion if clinically indicated.	If the patient had an IRR during the previous infusion, the subsequent infusion must be delivered over 60 ( $\pm$ 15) minutes.
Patients will be informed about the possibility of delayed post-infusion symptoms and instructed to contact their study physician if they develop such symptoms.	Record patient's vital signs (pulse rate, respiratory rate, blood pressure, and temperature) during the infusion or after the infusion if clinically indicated or if the patient experienced symptoms during the previous infusion.  If no reaction occurs, continue subsequent infusions over 30 ( $\pm$ 10) minutes using the same schedule for recording vital signs.

IRR=infusion-related reaction; NaCl=sodium chloride.

Dose modifications to atezolizumab are not permitted. Guidelines for treatment interruption of atezolizumab are provided in [Section 5.1.3.3](#), and the management of specific adverse events associated with cobimetinib and atezolizumab are provided in [Section 5.1.3.4](#). For information regarding management of atezolizumab-associated adverse events, refer to [Appendix 8](#).

For anaphylaxis precautions, see [Appendix 7](#).

See the pharmacy manual for detailed instructions on drug preparation, storage, and administration.

Any dose modification should be noted on the Study Drug Administration electronic Case Report Form (eCRF). Cases of accidental overdose or medication error, along with any associated adverse events, should be reported as described in [Section 5.4.4](#).

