#### **3.3.2 Rationale for Cobimetinib and Atezolizumab Dose and Schedule**

Concomitant administration of cobimetinib and atezolizumab was studied in Study GP28363. Cobimetinib and atezolizumab in combination were found to be safe and tolerable with cobimetinib on the approved dose and schedule of 60 mg QD 21/7

(Days 1–21 of a 28-day cycle), and atezolizumab 800 mg IV Q2W, which is equivalent in exposure to the approved dose and schedule for the treatment of bladder cancer of 1200 mg IV every 3 weeks (Q3W).

Cobimetinib will be administered at the approved dose and schedule of 60 mg QD for 21 days and 7 days off of each 28-day cycle. For administration with cobimetinib in this 28-day cycle, a dose of 840 mg atezolizumab will be administered Q2W. The 840-mg dose is expected to be similar to the 800-mg dose of atezolizumab and was selected in this study to simplify dose administration. Atezolizumab is formulated at a concentration of 60 mg/mL; thus, 800 mg corresponds to a volume of 13.33 mL. To ensure consistent, precise, and clinically feasible administration in this study, the volume was rounded up to 14 mL, corresponding to a dose of 840 mg. The 840-mg dose is not expected to result in meaningfully different exposures compared with the 800-mg dose.

In addition, the atezolizumab dose of 840 mg Q2W is equivalent to an average body weight–based dose of 15 mg/kg Q3W, the recommended Phase II dosage for atezolizumab based on nonclinical and clinical studies, and it has been used in multiple atezolizumab Phase III studies in other indications.

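### Table 3 tells sites to infuse one vial at the first atezolizumab infusion; the only vial described holds 1200 mg, which is 360 mg (43%) above the fixed 840-mg dose

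*Combined protocol and SAP*

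**What the plan says.** Section 4.3.2.2 sets the dose: "Atezolizumab will be given at a fixed dose of 840 mg by IV infusion on Days 1 and 15 of each 28-day cycle". Cohort 7 starts atezolizumab later but at the same amount; its patients "will receive the first dose of atezolizumab of 840 mg by IV infusions on Day 15 of Cycle 1". The section then hands over to the table: "Atezolizumab infusions will be administered per the instructions outlined in" Table 3.

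The First Infusion column of Table 3 says "Infuse atezolizumab (one vial in 250 mL of NaCl"), to run over 60 (±15) minutes. No mg or mL amount appears in that cell. The Subsequent Infusions column mentions no vial, volume or diluent.

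The vial is described once, in Section 4.3.1.2: "The vial is designed to deliver 20 mL (1200 mg) of atezolizumab solution". That section also gives the route from vial to dose: "Administration of 14 mL of atezolizumab solution from a 1200-mg vial contains an 840-mg dose". Section 3.3.2 agrees. It states a concentration of 60 mg/mL and explains that, starting from 800 mg, "the volume was rounded up to 14 mL, corresponding to a dose of 840 mg".

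Below Table 3 the protocol rules out atezolizumab dose modifications and adds: "See the pharmacy manual for detailed instructions on drug preparation, storage, and administration".

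**The concern.** The table that Section 4.3.2.2 names for giving infusions describes the quantity as a whole vial, and a whole vial is not the dose. No 840-mg vial is described anywhere in the protocol.

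Three things are at stake if a site prepares the full vial:

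- **Protocol compliance.** Section 5.4.4 defines giving more than the assigned dose by accident as an accidental overdose, to be recorded and reported to the sponsor within 24 hours whether or not an adverse event follows. A site could incur this by doing what the table says.
- **Pharmacokinetics.** In Appendix 2, the first infusion is one of only two that have a post-infusion atezolizumab sample; the other is Cycle 3 Day 15. Section 6.6 summarises maximum concentration by study day, and Section 3.3.6 plans a comparison with single-agent data. A wrong first dose would enter that summary directly.
- **Tolerability.** Table 3 does not allow premedication at this infusion, so the larger amount would go to patients receiving their first study infusion without it.

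**Working it through.** **Inputs**

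| Quantity | Value | Source |
|---|---|---|
| Fixed dose per infusion | 840 mg | Section 4.3.2.2 |
| Vial | 20 mL, 1200 mg | Section 4.3.1.2 |
| Volume for the dose | 14 mL | Sections 4.3.1.2 and 3.3.2 |
| Concentration | 60 mg/mL | Section 3.3.2 |
| Table 3, first infusion | one vial in 250 mL NaCl | Table 3 |

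**Step 1: reproduce the plan's own figures** (dose = volume × concentration).

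- Concentration implied by the vial: 1200 mg / 20 mL = 60 mg/mL, as stated.
- Volume for 800 mg: 800 / 60 = 13.33 mL, as stated in Section 3.3.2.
- Dose in 14 mL: 14 × 60 = 840 mg, as stated.

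Each stated figure is correct. The mismatch lies between the vial instruction and the dose.

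**Step 2: the literal Table 3 instruction.**

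- One full vial: 20 × 60 = 1200 mg.
- Excess: 1200 − 840 = 360 mg, or 20 − 14 = 6 mL.
- Relative excess: 360 / 840 = 42.9%.
- Conversely, the correct dose is 840 / 1200 = 70% of a vial.

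Section 4.3.1.2 notes that a vial may hold more than its stated volume, so emptying it could give slightly more than 1200 mg. The amount of overfill is not stated, and I have not counted it.

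**Step 3: Cycle 1 total if only the first infusion is affected.**

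- Cohorts 1–6 (two infusions in Cycle 1): (1200 + 840) / (840 + 840) = 2040 / 1680 = 1.214, or 21.4% more.
- Cohort 7 (one infusion in Cycle 1, on Day 15): 1200 / 840 = 1.429, or 42.9% more.

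The vial wording is confined to the First Infusion column, so the documents do not support carrying this on to later infusions.

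**Step 4: effect on the first post-infusion concentration.** This needs two assumptions: that concentration is proportional to dose, and that a fraction *p* of patients receive the full vial. The documents give no value for *p*. The cohort mean would then be raised by *p* × 42.9%: nothing at *p* = 0, 21.4% at *p* = 0.5 and 42.9% at *p* = 1.

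**The case against.** The strongest reply is that the protocol settles the matter itself. The 840-mg dose appears in the synopsis and in Sections 3.1.1.1, 3.3.2, 3.3.2.1 and 4.3.2.2. Section 4.3.1.2 gives the 14-mL volume, and the text under Table 3 rules out dose modification. Table 3 is mainly about premedication, vital signs and infusion time. Preparation is left to the pharmacy manual, which is cited both in Section 4.3.1.2 and below the table. Because vials are single-use, each 840-mg dose does consume exactly one, so the cell may have meant the number of vials opened.

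Much of this stands. The intended dose is clear, the practical risk is reduced, and this is a wording inconsistency, since no calculation in the protocol fails. But the repeated 840-mg statements show which text is wrong; they do not make the table right. The vial-count reading is possible but less natural, because the cell says to infuse the vial and not to draw from it. The pharmacy manual cannot be checked here.

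It is also fair to say that 1200 mg is a recognised single dose: Section 3.3.2 gives 1200 mg every 3 weeks as the approved bladder-cancer schedule and treats 800 mg every 2 weeks as equivalent in exposure. That argues against expecting serious harm from one such infusion. It also means that a full-vial preparation need not look wrong to pharmacy staff.

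**Conclusion.** The concern holds. Read literally, the First Infusion column of Table 3 gives 1200 mg against a fixed dose of 840 mg: 360 mg, or 42.9%, too much at one infusion per patient. This rests on Table 3 meaning the vial's full contents and on the vial being the one in Section 4.3.1.2, the only one described.

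It is a potential dosing error in an operative instruction. It is not evidence that 1200 mg was intended or given, and whether any site would act on it cannot be established from the documents. It should be fixed because it concerns the dose and the correction is trivial.

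**What to change.** In the First Infusion column of Table 3, replace the reference to one vial with 840 mg (14 mL) in 250 mL of NaCl. At 60 mg/mL this is exactly the fixed dose and leaves 6 mL (360 mg) of the vial's stated 20 mL unused. Confirm that the pharmacy manual gives the same amount, and notify sites of the correction.

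The cost is one line at the next amendment, one check of the manual and one site notice. Sample size and the planned analyses do not change.

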### **4.3.3 Investigational Medicinal Product Accountability**

All IMPs required for completion of this study (cobimetinib and atezolizumab) will be provided by the Sponsor where required by local health authority regulations. The study site will acknowledge receipt of IMPs, using the IxRS to confirm the shipment condition and content. Any damaged shipments will be replaced.

IMPs either will be disposed of at the study site according to the study site's institutional standard operating procedure or will be returned to the Sponsor with the appropriate documentation. The site's method of IMP destruction must be agreed to by the Sponsor. The site must obtain written authorization from the Sponsor before any IMP is destroyed, and IMP destruction must be documented on the appropriate form.

Accurate records of all IMPs received at, dispensed from, returned to, and disposed of by the study site should be recorded on the Drug Inventory Log.

### **4.3.4 Post-Trial Access to Cobimetinib and Atezolizumab**

The Sponsor will offer post-trial access to the study drug cobimetinib and atezolizumab free of charge to eligible patients in accordance with the Roche Global Policy on Continued Access to Investigational Medicinal Product, as outlined below.

A patient will be eligible to receive study drug after completing the study if all of the following conditions are met:

- The patient has a life-threatening or severe medical condition and requires continued study drug treatment for his or her well-being.
- There are no appropriate alternative treatments available to the patient.
- The patient and his or her doctor comply with and satisfy any legal or regulatory requirements that apply to them.

A patient will not be eligible to receive study drug after completing the study if any of the following conditions are met:

- The study drug is commercially marketed in the patient's country and is reasonably accessible to the patient (e.g., is covered by the patient's insurance or wouldn't otherwise create a financial hardship for the patient).
- The Sponsor has discontinued development of the study drug or data suggest that the study drug is not effective for the particular solid tumor depending on the cohort.
- The Sponsor has reasonable safety concerns regarding the study drug as treatment for the particular solid tumor, depending on the cohort.
- Provision of study drug is not permitted under the laws and regulations of the patient's country.

The Roche Global Policy on Continued Access to Investigational Medicinal Product is available at the following Web site:

[http://www.roche.com/policy\\_continued\\_access\\_to\\_investigational\\_medicines.pdf](http://www.roche.com/policy_continued_access_to_investigational_medicines.pdf)

#### **4.4 CONCOMITANT THERAPY**

Concomitant therapy includes any medication (e.g., prescription drugs, over-the-counter drugs, vaccines, herbal or homeopathic remedies, nutritional supplements) used by a patient from 7 days prior to initiation of study drug to the study completion or discontinuation visit. All such medications should be reported to the investigator and recorded on the Concomitant Medications eCRF.

##### **4.4.1 Permitted Therapy**

Patients are permitted to use the following therapies during the study:

- Hormonal therapy with gonadotropin-releasing hormone agonists for prostate cancer
- Oral contraceptives
- Hormone-replacement therapy
- Prophylactic or therapeutic anticoagulation therapy (such as warfarin at a stable dose or low-molecular-weight heparin). However, caution should be used in patients on anticoagulation therapy because of the risk of hemorrhage events with cobimetinib.
- Inactivated influenza vaccinations
- Megestrol administered as an appetite stimulant
- Mineralocorticoids (e.g., fludrocortisone)
- Corticosteroids administered for chronic obstructive pulmonary disease or asthma
- Low-dose corticosteroids administered for orthostatic hypotension or adrenocortical insufficiency
- Palliative radiotherapy (e.g., treatment of known bone metastases or symptomatic relief of pain) as outlined below:

Palliative radiotherapy is permitted, provided it does not interfere with the assessment of the tumor target lesions.

- Radiotherapy to the brain as outlined below:

Patients whose extracranial tumor burden is stable or responding to study treatment and who are subsequently found to have three or fewer brain metastases may receive radiotherapy to the brain (either stereotactic radiosurgery or whole-brain radiation therapy) provided that all of the following criteria are met:

- The patient has no evidence of progression or hemorrhage after completion of CNS-directed therapy.
- The patient has no ongoing requirement for corticosteroids as therapy for CNS disease.

Patients who require corticosteroid therapy for more than 7 days after completion of radiotherapy must be discontinued from study treatment.

- Anti-convulsant therapy, if required, is administered at a stable dose.

Premedication with antihistamines, antipyretic medications, and/or analgesics may be administered for the second and subsequent atezolizumab infusions only, at the discretion of the investigator. Anti-emetic and anti-diarrheal medications should not be administered prophylactically before initial treatment with study drugs. At the discretion of the investigator, prophylactic anti-emetic and anti-diarrheal medication(s) may be used per standard clinical practice before subsequent doses of study drugs. Hematopoietic growth factors should not be administered prophylactically before initial treatment with study drugs. Hematopoietic growth factors may be administered according to local guidelines if indicated during the study.

In general, investigators should manage a patient's care with supportive therapies as clinically indicated, per local standard practice. Patients who experience infusion-associated symptoms may be treated symptomatically with acetaminophen, ibuprofen, diphenhydramine, and/or H2-receptor antagonists (e.g., famotidine, cimetidine), or equivalent medications per local standard practice. Serious infusion-associated events manifested by dyspnea, hypotension, wheezing, bronchospasm, tachycardia, reduced oxygen saturation, or respiratory distress should be managed with supportive therapies as clinically indicated (e.g., supplemental oxygen and  $\beta_2$ -adrenergic agonists; see [Appendix 7](#)).

